### **Sleep Efficiency**

Sleep efficiency is the total number of minutes marked as sleep during the total length of the sleep period in minutes.

$$\frac{\text{sleep time in minutes}}{\text{Total minutes of sleep period (sleep minutes + awake minutes)}}$$

## 5.1.6 Safety Endpoints

### **Serious Adverse Event (SAE)**

An event categorized as “Adverse Event” with the indicator flag “Serious” equal to “Yes” on the Events eCRF starting on or after signing of the informed consent and up to the End of Study date

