### **Treatment-Emergent Adverse Event (TEAE)**

An event categorized as “Adverse Event” on the Events eCRF starting on or after first dose of investigational product, as determined by “Did event start before first dose of investigational product” equal to “No” or missing, and up to the End of Study date.

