### **Serious Treatment-emergent Adverse Event**

A treatment-emergent adverse event with the indicator flag “Serious” equal to “Yes” on the Events eCRF

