### **9.6.2 Adverse Events**

The Medical Dictionary for Regulatory Activities (MedDRA) version 22.0 or later will be used to code all adverse events (AEs) to a system organ class (SOC) and a preferred term (PT). All AEs will be graded using the Common Terminology Criteria for Adverse Events (CTCAE) Version 4.03. All AE summary tables described below will be summarized by treatment group using subject incidence.

The subject incidence of AEs will be summarized for all treatment-emergent adverse events (TEAEs), serious AEs, AEs leading to withdrawal of investigational product, fatal AEs, and adverse events of interest (EOI) including

- Ischaemic Central Nervous System Vascular Conditions SMQ (Narrow)
- Ischaemic Heart Disease SMQ (Narrow and Broad)
- Peripheral Arterial Disease AMQ (Narrow)
- Hypertension SMQ (Narrow and Broad)
- Constipation AMQ (Narrow and Broad)
- Alopecias AMQ (Broad)

Subject incidence of all TEAEs, SAEs, AEs leading to withdrawal of investigational product, fatal AEs, and device related AEs will be tabulated by SOC in alphabetical order and PT in descending order of frequency.

Subject incidence of EOI (standardized MedDRA queries [SMQ] and/or Amgen medical queries [AMQ]) will also be summarized according to their categories and PT in descending order of frequency.

In addition, summaries of all TEAEs and SAEs occurring in at least 3% of the subjects by PT in any treatment arm will be provided in descending order of frequency.

Summaries of all TEAEs and SAEs will be tabulated by SOC, PT, and grade.

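### By-arm SAE tables in SAP 9.6.2 use a definition that starts at informed consent, so read literally they count pre-dose events; the defined serious treatment-emergent category is used in no planned table

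*SAP*

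**What the plan says.** SAP 5.1.6 gives three definitions that matter here.

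- **SAE:** an adverse event flagged serious, "starting on or after signing of the informed consent and up to the End of Study date".
- **TEAE:** an adverse event "starting on or after first dose of investigational product, as determined by" an eCRF question on whether the event began before first dose.
- **Serious treatment-emergent event:** "A treatment-emergent adverse event with the indicator flag “Serious” equal to “Yes” on the Events eCRF".

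SAP 9.6.2 sets the presentation: "All AE summary tables described below will be summarized by treatment group using subject incidence". It then plans four sets of tables that name serious events:

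- an overall incidence summary;
- a table by system organ class and preferred term: "Subject incidence of all TEAEs, SAEs, AEs leading to withdrawal of investigational product, fatal AEs, and device related AEs will be tabulated by SOC";
- a preferred-term table for events in at least 3% of subjects in any arm;
- a graded table: "Summaries of all TEAEs and SAEs will be tabulated by SOC, PT, and grade".

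All four refer to serious AEs or SAEs. The serious treatment-emergent category appears only where it is defined.

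SAP 6.3 and 9.6.1 restrict these tables to randomized subjects who received at least one dose. Protocol 9.2.3.1.1.1 collects adverse events from first dose, whereas Protocol 9.2.3.1.1.2 collects serious ones from consent. Pre-dose SAEs will therefore be in the database. Protocol 10.4.2.2.1 also plans SAE tables without limiting them to treatment-emergent events.

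**The concern.** A programmer who applies the SAP's own definition of an SAE would count a hospitalization during screening or baseline in the erenumab or placebo column, provided the subject was later randomized and dosed. Study drug cannot have caused such an event.

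Two things are at stake. First, the SAE and TEAE tables would cover different periods. A subject could appear in the SAE table and not in the TEAE table, and the study report would have to explain why. Second, serious events are likely to be few at this sample size, so one or two pre-dose events could visibly change the counts that a reader compares between arms.

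**Working it through.** **1. Does any text limit the SAE tables to post-dose events?**

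| Place | What it restricts | Limits event timing? |
|---|---|---|
| SAP 6.3 and 9.6.1 (Safety Analysis Set) | subjects: randomized and dosed | No |
| SAP 5.6 (subject incidence) | counts within a given period, over subjects entering it | No period is named for the SAE tables |
| SAP 7 (planned analyses) | reporting by double-blind treatment group | Sets the columns, not the onset window |
| Protocol 10.4.2.2.1 | lists SAE tables | No |

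Nothing overrides the definition in SAP 5.1.6.

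**2. Length of the two windows**

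Inputs:
- initial screening, up to 3 weeks, and baseline, 4 weeks (Protocol 9.1.1.1);
- baseline window of +7 days (Protocol Table 2-1, footnote b);
- treatment period, 24 weeks (Protocol 5.1).

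The protocol's own total is reproduced: 3 + 4 + 24 = 31 weeks, as stated in Protocol 5.3.2.

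Pre-dose share of the SAE window = pre-dose time / (pre-dose time + treatment time):
- 28-day baseline only: 28 / (28 + 168) = 14.3%
- full 7 weeks: 7 / 31 = 22.6%
- 7 weeks plus the 7-day window: 56 / (56 + 168) = 25.0%

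**3. What this could mean in subjects**

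The documents give no SAE rate, so the rates here are assumptions. Assume a constant hazard with 24-week risk r, and 120 subjects per arm (SAP 3.2). Expected pre-dose subjects per arm = 120 × [1 − (1 − r)^(w/24)], where w is the number of pre-dose weeks.

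| Assumed r | On-treatment subjects per arm (120 × r) | Pre-dose, w = 4 | w = 7 | w = 8 |
|---|---|---|---|---|
| 1% | 1.2 | 0.20 | 0.35 | 0.40 |
| 2% | 2.4 | 0.40 | 0.71 | 0.81 |
| 3% | 3.6 | 0.61 | 1.06 | 1.21 |
| 5% | 6.0 | 1.02 | 1.78 | 2.03 |

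These are upper-end values, because the formula ignores screen failure. At 2% to 3%, an arm would have about 2 to 4 subjects with an on-treatment SAE. If one pre-dose event did enter an arm, its count would rise by 1/4 = 25% to 1/2 = 50%.

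**4. Effect on the comparison**

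Assume serious treatment-emergent risks of 4% and 2%, and a background of 2% per 24 weeks before dosing in both arms. Let p = 1 − 0.98^(w/24). The incidence over the whole window is 1 − (1 − risk)(1 − p).

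| w | Arm with 4% risk | Arm with 2% risk | Risk ratio | Risk difference |
|---|---|---|---|---|
| 0 (post-dose only) | 4.00% | 2.00% | 2.00 | 2.00 points |
| 4 | 4.32% | 2.33% | 1.86 | 1.99 points |
| 7 | 4.56% | 2.58% | 1.77 | 1.98 points |
| 8 | 4.64% | 2.66% | 1.75 | 1.98 points |

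The ratio moves toward 1, while the difference barely moves.

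**The case against.** The strongest reply is that the wording is shorthand. SAP 9.6.2 does not repeat defined labels faithfully elsewhere: SAP 5.1.6 defines a treatment-emergent adverse device effect, yet 9.6.2 speaks only of device-related AEs. A serious treatment-emergent category would hardly be defined unless some table was meant to use it. This may well be what the authors intended. But SAE has its own definition with a different start date, and the SAP nowhere says that the term means something else in 9.6.2. The ambiguity stands.

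A second reply is that the SAE window follows the protocol, which collects SAEs from consent and plans SAE tables without a treatment-emergent limit. That is correct, and it is a good reason to report every pre-dose SAE. It does not require placing them in by-arm incidence.

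A reader might infer that the plan attributes pre-dose events to study drug. It does not. Tabulation under a randomized arm is not a causal judgement: the investigator assesses causality event by event (Protocol 12.4), and onset before first dose is recorded on the eCRF. A reader might also infer that up to a quarter of tabulated SAEs would be pre-dose. The 25% is a maximum share of time. A subject with a serious event before dosing must still pass the Part 2 criteria, including exclusions 226 and 230, to enter these tables, and some would not.

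**Conclusion.** The point holds as a minor defect of definition. Read literally, SAP 9.6.2 counts SAEs with onset before first dose in the by-arm incidence of dosed subjects. The SAE tables then span up to 31 weeks (32 with the baseline window) against 24 for the TEAE tables, and are not a subset of them.

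The pre-dose part is 14% to 25% of the SAE window in calendar time; its share of events is probably smaller. It is tempting to conclude that this biases the safety comparison, but the documents do not support that. Pre-dose events come before treatment and balance between arms in expectation, so the expected risk difference is essentially unchanged. What remains is chance noise and a ratio closer to 1: 1.75 to 1.86 instead of 2.0 under the assumed rates. SAP 9.6.1 plans no statistical comparison of safety, so no test result can change.

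The window shares rest on the documents' own figures. The subject counts and risk ratios rest on assumed SAE rates and a constant hazard.

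**What to change.** In SAP 9.6.2, replace serious AEs and SAEs with serious treatment-emergent adverse events, as defined in 5.1.6, in all four sets of by-arm tables: overall summary, organ class and preferred term, at least 3% by preferred term, and grade. Add a separate listing of SAEs with onset before first dose, so that everything collected from consent is still reported.

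The fatal-event and IP-withdrawal tables need no more than consistent wording. A dosed subject cannot have died before dosing, and withdrawal of IP presupposes a dose, so hardly any event would move.

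The cost is a wording change in one SAP section and one extra listing. The filter already exists in the eCRF question used for the TEAE definition. No new data and no protocol amendment are needed. The change should be made before database lock.

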### **Treatment-Emergent Adverse Event (TEAE)**

An event categorized as “Adverse Event” on the Events eCRF starting on or after first dose of investigational product, as determined by “Did event start before first dose of investigational product” equal to “No” or missing, and up to the End of Study date.

### **Serious Treatment-emergent Adverse Event**

A treatment-emergent adverse event with the indicator flag “Serious” equal to “Yes” on the Events eCRF

### **Treatment-emergent Adverse Device Effect**

A treatment-emergent adverse event with the indicator flag “Is there a reasonable possibility that the event may have been caused by the investigational device” equal to “Yes” on the Events eCRF

## 5.2 Study Dates

### **Informed Consent Date**

The date on which subject signs the informed consent form.

### **Date of Device Ready for Entry**

The date on which an eDiary device is ready for entry after completion of initial screening.

### **Randomization (Enrollment) Date**

Randomization (Enrollment) Date is the date on which a subject is assigned to one of the treatments through Interactive Response Technology (IRT).

### **First IP Dose Date**

First IP Dose Date is the date on which a subject is administered the first dose of IP following randomization as recorded on the IP Administration eCRF. The first IP dose may be the same day or after the randomization date.

### **Last IP Dose Date**

Last IP Dose Date is the date on which a subject is administered the last dose of IP as recorded on the IP Administration eCRF.

### **End of Study (EOS) Date**

End of study (EOS) date is defined as the last date on which the subject participates in the study as recorded on the End of Study eCRF.

## **5.3 Study Points of Reference**

### **Baseline Assessment**

Baseline assessment for the endpoint of the interest is defined as the last non-missing measurement taken or the monthly interval assessed (for endpoints derived from daily and weekly eDiary collection) before the first dose of investigational product. In cases where baseline measurements are taken on the same day as IP, it will be assumed that these measurements are taken prior to IP being administered. For subjects who are randomized but not dosed after the randomization, the baseline of the study is defined as the last non-missing measurement prior to or on the date of randomization.

### **Study Day 1**

Study Day 1 is defined as the first IP dose date. For subjects who are randomized but not dosed after randomization, the Study Day 1 is defined as the date of randomization.

### **Study Day**

Study Day is defined as the number of days from Study Day 1.

Before Study Day 1:

$$\text{Study Day} = (\text{Date of Interest} - \text{Date of Study Day 1})$$

On or after Study Day 1:

$$\text{Study Day} = (\text{Date of Interest} - \text{Date of Study Day 1}) + 1$$

Therefore, the day prior to Study Day 1 is -1.

## **5.4 Study Time Intervals**

### **5.4.1 Monthly Intervals for Efficacy Endpoints Derived From Daily, Weekly, or Wearable Data Collection**

The (4-week) monthly intervals for efficacy endpoints derived from daily eDiary collection, weekly collection for WPAI, or wearable device (physical activity data only) will be determined based on each subject's monthly IP dosing dates. When an IP is

missed, discontinued, or no longer required, a 28-day monthly interval will be used. Any eDiary or wearable data occurring after EOS date will not be included in the analysis.

Applicable efficacy endpoints utilizing the monthly intervals in [Table 5-1](#) include:

- Monthly migraine days (MMD)
- Monthly headache days (MHD)
- Monthly percent work impairment as measured by WPAI
- Monthly average daily proportion of time spent in each physical activity category: sedentary, light, lifestyle, moderate, vigorous, and very vigorous

**Table 5-1. Monthly Intervals for Efficacy Endpoints Derived From Daily, Weekly, or Physical Activity Wearable Data Collection**

Study Period	Assessment Timepoint	Monthly Interval	
		Start Date (Day) a	End Date (Day) b
Baseline Period	Baseline	Date of device ready for entry c	Day prior to study day 1
Double-blind Treatment Period	Week 4 (Month 1)	Study Day 1	Week 4 dose date – 1
	Week 8 (Month 2)	Week 4 dose date	Week 8 dose date – 1
	Week 12 (Month 3)	Week 8 dose date	Week 12 dose date – 1
	Week 16 (Month 4)	Week 12 dose date	Week 16 dose date – 1
	Week 20 (Month 5)	Week 16 dose date	Week 20 dose date – 1
	Week 24 (Month 6)	Week 20 dose date	Week 20 dose date + 27

a Start Date (Day) = End date (day) of previous monthly interval + 1 if IP dose date is not available

b End Date (Day) = Start date (day) of current monthly interval + 27 if IP dose date is not available

c For physical activity wearable data, Baseline Start Date (day) is defined as Max (Earliest valid activity date, week -4 visit date)

Sleep associated endpoints from each sleep period will utilize the monthly intervals defined in [Table 5-2](#) based on the sleep start date/time.

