**Page 22 of 101**

---

Health Questionnaire; PSQI = Pittsburgh Sleep Quality Index; PVT = Psychomotor Vigilance Test; Wk = week; WPAI = Work Productivity and Activity Impairment Questionnaire

a The initial screening period is up to 3 weeks (21 days) before the baseline period begins.

b Each study visit during the double-blind treatment period (DBTP) has a window of  $\pm 3$  consecutive calendar days. The baseline period has a window of + 7 consecutive calendar days; the day 1 visit must occur 28 to 35 days after the week -4 visit date. All study visit target dates are to be calculated from the day 1 visit date. All study procedures for a given study visit are to be completed on the same day.

c A subject who discontinues the study during the DBTP (before week 24) will complete the assessments of the week 24/EOS visit.

d Format of these questionnaires will be electronic for the DCTS (within DCTS hand-held device).

e For subjects who provided informed consent for the pharmacogenetic studies, DNA will be obtained from the cell pellet collected in the plasma tube used for the biomarker development sample. Therefore, additional sampling is not required.

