#### **9.1.2 Treatment Period**

Study visits will occur per the Schedule of Activities ([Table 2-1](#)). The date of the first dose of IP is defined as day 1 and must occur 28 to 35 days from the Day -28 visit. On-study visits after Day 1 may be completed within  $\pm 3$  days. All subsequent doses and study visits will be scheduled based on the day 1 date. Administration of protocol-required therapies is to be administered once every 4 weeks during each visit that it is required.

Subjects who discontinue IP are encouraged to remain in the study and complete all remaining procedures and study visits.

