**Table 5-2. Monthly Intervals for Sleep Associated Endpoints**

Study Period	Assessment Timepoint	Monthly Interval	
		Start Date/Time a	End Date/Time b
Baseline Period	Baseline	Max (Earliest recorded sleep start date, week -4 visit date)	Day 1 dose date/time
Double-blind Treatment Period	Week 4 (Month 1)	Day 1 dose date/time	Week 4 dose date/time
	Week 8 (Month 2)	Week 4 dose date/time	Week 8 dose date/time
	Week 12 (Month 3)	Week 8 dose date/time	Week 12 dose date/time
	Week 16 (Month 4)	Week 12 dose date/time	Week 16 dose date/time
	Week 20 (Month 5)	Week 16 dose date/time	Week 20 dose date/time
	Week 24 (Month 6)	Week 20 dose date/time	≤ Week 24 visit date

a Start Date/Time = End date/time of previous monthly interval if IP dose date is not available

b End Date/Time = Start date/time of current monthly interval + 27 if IP dose date is not available

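### Two SAP interval rules give the wrong month length: Table 5-1 when a dose falls far outside the visit window, Table 5-2 when a dose date is unavailable (minor)

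*SAP*

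**What the plan says.** **Diary, WPAI and physical activity data.** SAP 5.4.1 states that the intervals "will be determined based on each subject's monthly IP dosing dates". In Table 5-1 each month ends the day before the next dose; month 2, for example, ends at "Week 8 dose date – 1". The fallback is for a dose that is "missed, discontinued, or no longer required, a 28-day monthly interval will be used". Footnote b implements it: "End Date (Day) = Start date (day) of current monthly interval + 27 if IP dose date is not available". Under footnote a, the next month then starts one day after the previous end.

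**Dosing calendar.** Protocol 9.1.2: "All subsequent doses and study visits will be scheduled based on the day 1 date". Footnote b of the Schedule of Activities sets the tolerance: "Each study visit during the double-blind treatment period (DBTP) has a window of" plus or minus 3 calendar days.

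**Minimum data.** Under SAP 5.1.1 and 8.3, monthly migraine days (MMD) are set to missing with fewer than 14 diary days, whatever the length of the interval. SAP 5.1.2 needs at least 2 weekly WPAI scores per month. SAP 5.1.5 needs at least 14 valid wearable days.

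**Sleep data.** Table 5-2 uses date/time limits. Footnote a: "Start Date/Time = End date/time of previous monthly interval if IP dose date is not available". Footnote b: "End Date/Time = Start date/time of current monthly interval + 27 if IP dose date is not available".

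**The concern.** A late dose has a date, so the fallback in Table 5-1 does not apply to it, and the SAP sets no limit on how late a dose may be and still define a boundary. The next dose returns to the day-1 calendar. The month before the late dose is therefore stretched and the month after it is cut short. The 14-day minimum does not scale with interval length, so a month can be too short to qualify even when every diary was completed.

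MMD and WPAI over months 4 to 6 are the first two secondary endpoints in the testing sequence, and their estimands apply regardless of adherence. A rule that drops observed data because a dose was late fits poorly with that.

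The sleep table repeats the + 27 of Table 5-1 without the one-day step between months that makes it come to 28.

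**Working it through.** **Inputs.** Target dose days are 1, 29, 57, 85, 113 and 141, with week 24 on day 169 (Protocol 9.1.2; target days in SAP Table 5-3). The visit window is ±3 days. The unit of + 27 in Table 5-2 is not given and is taken as days.

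**Step 1: the plan's own figure.** Table 5-1 fallback: start + 27, both ends included, is 28 days, and the next month starts at end + 1. With the week-8 dose missed, month 2 is days 29-56 and month 3 is days 57-84, and all six months are 28 days. The stated 28 days is reproduced.

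**Step 2: doses inside the window.** The shortest month has its opening dose 3 days late and the next 3 days early: 28 - 6 = 22 days. The longest is 28 + 6 = 34. Enumerating offsets of -3, 0 and +3 days with every pattern of missed doses keeps all months between 22 and 34 days. A 22-day month holds 3 or 4 weekly WPAI scores.

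**Step 3: a late week-12 dose, with weeks 8 and 16 on target.** The dose falls on day 85 + L. Month 3 is days 57 to 84 + L, so 28 + L days. Month 4 is days 85 + L to 112, so 28 - L days.

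| L (days late) | Month 3 | Month 4 | Month-4 MMD with complete diaries |
|---|---|---|---|
| 3 | 31 | 25 | kept |
| 7 | 35 | 21 | kept |
| 10 | 38 | 18 | kept |
| 14 | 42 | 14 | kept |
| 15 | 43 | 13 | missing |
| 19 | 47 | 9 | missing |

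If the next dose is e days early, a complete month is lost when 28 - L - e < 14. That is L ≥ 15 for e = 0, L ≥ 12 for e = 3, and L ≥ 18 if the next dose is 3 days late (e = -3).

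**Step 4: WPAI and month 6.** With one score every 7 days, 14 days always hold 2 scores, 8 to 13 days hold 1 or 2, and 7 days hold 1. WPAI may therefore fall below its minimum in a shortened month, but need not. Month 6 is cut at end of study: with that on day 169, a week-20 dose 16 days late leaves days 157-169, which is 13 days.

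**Step 5: which late doses touch months 4 to 6.** A late week-4 or week-8 dose changes only months 1 to 3. Late week-16 and week-20 doses move days within months 4 to 6. Only a late week-12 dose moves days across the month 3/4 boundary and out of the endpoint window.

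**Step 6: sleep.** With all doses on target, Table 5-2 gives 28 days each month (day 1 to 29, 29 to 57, and so on). With a dose date unavailable, end = start + 27 and next start = previous end, so the month is 27 days.

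- Week-8 dose missed: month 2 runs from 29 to 56 (27 days) and month 3 from 56 to 85 (29 days).
- Dosing stopped after week 4: months 2 to 5 are 27 days each, and month 6 runs from 137 to 169 (32 days).
- Day-1 dose only: boundaries at 1, 28, 55, 82, 109 and 136. The week-20 boundary is 141 - 136 = 5 days early, and month 6 is 169 - 136 = 33 days.

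**Step 7: bound on power.** The SAP's inputs are 120 per group, two-sided 0.05, MMD -2.0 with SD 3.4, and WPAI -10.0 with SD 23.1. They give 99.5% (stated as above 99%) and 91.8% (stated as 91%). The frequency of long delays is not in the documents. As an assumed range, suppose that 1%, 5% or 10% of subjects were lost entirely, which is harsher than losing one month. Power is then 99.5%, 99.3% or 99.1% for MMD, and 91.6%, 90.5% or 88.9% for WPAI.

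**The case against.** The strongest reply is that the loss needs an extreme case: a dose about 15 days late followed by one on schedule, so two doses about 13 days apart. The documents do not say that a dose so late would be given rather than recorded as missed, and a missed dose triggers the 28-day rule. Amendment 3 also allowed self-injection at traditional sites under COVID-19 restrictions, and the SAP plans to summarize COVID-related missed doses, the case that Table 5-1 handles. This stands as a limit on reach. It does not supply the missing rule.

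Unequal lengths are also partly absorbed. MMD is prorated to 28 days, WPAI is a mean of weekly scores, days moved into month 3 stay in the same mixed model, and a subject without month 4 still contributes other months. That stands too, but proration cannot recover a month set to missing.

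Anchoring months to doses is a legitimate choice, and a cut-off at the visit window gives it up from a 4-day deviation to cure a loss that starts at 12 to 15 days. That is a fair point about where to put the limit, not about whether to have one.

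A reader might infer that the dose-based months also make MMD and MFIQ inconsistent. The documents do not support much here: MFIQ has a 7-day recall, so it never covers the same days as a diary month.

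**Conclusion.** A minor correction: each rule as written gives a wrong interval in an identifiable case.

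- **Table 5-1.** A dose well outside the window still sets the boundary. A complete MMD month is lost only from about 15 days late (12 if the next dose is 3 days early). WPAI may also drop below 2 scores, and the exploratory physical activity measures use the same intervals.
- **Table 5-2.** Fallback months are 27 days, and the drift grows over consecutive missing doses to at most 5 days at the week-20 boundary. Only the exploratory sleep endpoint is affected.

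Three stronger readings are tempting and are not supported. Ordinary scheduling variation does not discard complete months, since the shortest in-window month is 22 days. Missed doses do not break Table 5-1, which returns 28 days. Sleep months are not 27 days in general, only when a dose date is unavailable. Nor can a number of affected subjects be stated, because the documents give no rate of long delays.

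The primary endpoint and MFIQ use the fixed windows of Table 5-3 and are untouched. The effect on power is likely small; the figures in step 7 rest on assumed loss rates.

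**What to change.** 1. **Table 5-1, footnotes a and b.** State that, for building analysis intervals only, a dose date outside the protocol visit window is treated as not available, so that the existing 28-day rule applies. With a late week-12 dose and the week-8 and week-16 doses on target, month 3 then ends on day 84 and month 4 is days 85-112, the same as if the dose had been skipped. If the week-8 dose was itself on day 60, month 3 is days 60-87 and month 4 is days 88-112 (25 days), which is still usable. If the sponsor prefers to keep more dose anchoring, a wider stated limit of up to 11 days late also keeps a complete month when the next dose is at most 3 days early (28 - 11 - 3 = 14).
2. **Table 5-2, footnote b.** Change + 27 to + 28 days. Each fallback sleep month before the last is then 28 days, unless the next available dose ends it, and the drift disappears.

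The cost is two footnote edits and minor programming, to be made before unblinding. The downside is that a few intervals will no longer start on the actual dose date. Nothing about dosing or visit scheduling changes.

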**5.1.2 Efficacy Endpoints Based on Weekly Collection**

**Work Productivity and Activity Impairment (WPAI) Questionnaire**

In the WPAI-Migraine questionnaire, subjects are asked 6 questions about work and activity impairment due to their migraine, including hours worked and hours missed in the last 7 days. The questionnaire will be collected weekly during baseline and post-baseline.

The weekly percent work impairment score is calculated based on questions 2, 4 and 5. Higher score indicates worse outcome.

The monthly percent work impairment equals to the arithmetic mean of the observed weekly percent work impairment scores over the monthly interval, if the number of weekly scores during baseline period or each of the monthly interval during post-baseline is ≥ 2. Otherwise, monthly measurement will be set to missing.

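### Weekly WPAI scores with a 7-day recall are filed by completion date into intervals built for daily data, so a score completed on a dose date counts in the wrong month

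*SAP*

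**What the plan says.** SAP 5.1.2 describes WPAI as asking about work and activity, "including hours worked and hours missed in the last 7 days". On timing it says only this: "The questionnaire will be collected weekly during baseline and post-baseline". Neither the SAP nor the protocol gives the weekday, or the date from which the weeks are counted.

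SAP 5.4.1 applies one set of dose-date intervals to "efficacy endpoints derived from daily eDiary collection, weekly collection for WPAI", and to wearable activity data. Its list of endpoints that use Table 5-1 includes "Monthly percent work impairment as measured by WPAI". In Table 5-1:

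- baseline ends on the "Day prior to study day 1";
- month 1 starts on Study Day 1, and each later month starts on a dose date;
- month 6 ends at "Week 20 dose date + 27".

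SAP 5.3 has two statements that bear on a Day 1 score. For daily and weekly diary endpoints, baseline is "the monthly interval assessed (for endpoints derived from daily and weekly eDiary collection) before the first dose of investigational product". For baseline measurements taken on the day of dosing, "it will be assumed that these measurements are taken prior to IP being administered".

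SAP Table 5-3 treats MFIQ, which also looks back 7 days (SAP 5.1.3), as a visit measure. The last value on or before Day 1 is baseline, the month 1 target is Day 29 and the month 6 target is Day 169.

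**The concern.** Cutting at the dose date suits a migraine day, which belongs to the calendar day on which it occurs. It does not suit a score that looks back a week: one completed on or just after a dose date describes mostly the interval that has closed. No rule in the SAP links a WPAI score to the week it describes.

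WPAI work impairment is third in the fixed testing sequence and is also reported month by month as an exploratory endpoint. At stake are the purity of the month 1 result, the number of scores behind the baseline covariate, use of the last treated week, and whether two programmers would place a Day 1 score in the same interval.

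**Working it through.** **1. The plan's own figure.** SAP Table 3-1 assumes a WPAI effect of -10.0, SD 23.1 and 120 per group, with two-sided alpha 0.05, and states 91% power. Power = Φ(Δ / (σ√(2/n)) − 1.96). Here 23.1 × √(2/120) = 2.982, 10/2.982 = 3.353, and Φ(1.393) = 91.8%. The noncentral t gives 91.6%. The stated figure is reproduced.

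**2. The same days under the two tables**, with on-time dosing:

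| Completed on | MFIQ (Table 5-3) | WPAI (Table 5-1) |
|---|---|---|
| Day 1 | baseline | month 1 |
| Day 29 (Week 4 dose) | month 1 | month 2 |
| Day 169 | month 6 | no month (141 + 27 = 168) |

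**3. Month 1.** Assume weekly scores, with recall covering the 7 days before completion. If the first score falls d days after Day 1, month 1 holds 7 − d untreated days out of 28. For illustration only, take the planning effect and SD as the month 1 values and let the effect scale with treated days.

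| First score | Untreated days | Share | Effect | Power |
|---|---|---|---|---|
| Day 1 | 7 | 25.0% | -7.5 | 71.1% |
| Day 2 | 6 | 21.4% | -7.9 | 75.0% |
| Day 4 | 4 | 14.3% | -8.6 | 82.0% |
| Day 7 | 1 | 3.6% | -9.6 | 89.9% |

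If recall includes the completion day, each untreated count falls by 1.

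**4. Baseline.** The protocol's Schedule of Activities allows 28 to 35 days between the week -4 visit and Day 1. If weeks are counted from the week -4 visit, a 28-day baseline puts the fourth score on Day 1, leaving 3 in baseline. With independent weekly errors, the error variance of the baseline mean becomes σ²/3 rather than σ²/4, one third larger. A 35-day baseline also puts a score on Day 1 but leaves 4 in baseline. Lengths of 29 to 34 days leave 4 in baseline and put 1 to 6 untreated days into month 1.

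**5. Month 6.** Visits may vary by 3 days either way. A Day 169 score is excluded if the Week 20 dose falls on Days 138 to 141 (month 6 ends on Days 165 to 168). It is included if the dose falls on Days 142 to 144 (month 6 ends on Days 169 to 171).

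**6. The tested contrast, months 4-6.** With scores on Days 1, 8, 15 and so on, the 12 scores run from Day 85 to Day 162 and describe Days 78-161 instead of Days 85-168. No untreated day enters at any weekly offset. One week of 12 comes from month 3. The documents give no month 3 effect; if it were 70% to 90% of the plateau, the bias would be (1/12) × (10% to 30%) × 10 = 0.08 to 0.25 points. At an effect of -9.75, 9.75/2.982 = 3.269 and Φ(1.309) = 90.5%.

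**The case against.** The best defence is that the entry day is unknown and one plausible schedule shows no fault. SAP 5.1.1 describes a mandatory evening diary. Suppose WPAI is completed on the evening of each seventh day (Days -22, -15, -8, -1, 7, 14, … 168) and recall includes that day. Every recall window then lies inside its Table 5-1 interval, baseline has 4 scores, and Day 168 is the last day of month 6. This stands as a possibility. It needs exact 28-day spacing, though, whereas baseline may run to 35 days and visits may move by 3 days. Nothing in either document fixes this schedule.

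A reader might infer that the SAP contradicts itself on the Day 1 score. It does not strictly do so. SAP 5.3 refers weekly diary endpoints to the pre-dose monthly interval, which Table 5-1 closes on Day -1, and the same-day sentence can be read as meant for visit questionnaires. The two statements are in tension and should be reconciled.

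A reader might also infer that the confirmatory WPAI test is compromised. The documents do not support that. Months 4-6 hold 12 possible scores and no untreated days at every offset. The same rule applies to both randomized arms, and the shift is toward no effect if the effect is still growing at month 3. Fewer baseline scores cost some precision without biasing the comparison.

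The defence does not explain why WPAI and MFIQ, with the same recall, are placed in different months when completed on the same day.

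**Conclusion.** The point holds as a misfit between the recall period and the interval rule, with limited consequences. On a dose date, Table 5-1 files a WPAI score in the month that is starting, although the score describes the month just ended. It drops a score completed 28 days after the Week 20 dose, which on schedule is the SAP's own Week 24 target day.

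The limits are:

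- up to 1 of 4 month 1 scores wholly untreated, a 25% dilution of an exploratory by-month result;
- 3 baseline scores instead of 4 when baseline is 28 days and a score falls on Day 1;
- a shift of up to one week in the tested months 4-6 window, worth at most about 0.25 of -10, with power about 90.5% against 91.8% in that worst case.

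It would go too far to say that an untreated week always enters month 1 or that the last treated week is always lost. The first needs a score on Day 1. The second needs a score on Day 169 and a Week 20 dose that is not late. The figures assume filing by completion date, recall that excludes the completion day, dilution proportional to treated days, and a month 3 effect of 70% to 90% of plateau.

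**What to change.** In SAP 5.4.1, give WPAI its own intervals:

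- A score completed on a dose date belongs to the interval just ended. A Day 1 score is then baseline, in line with the same-day rule in SAP 5.3 and with Table 5-3.
- Month 6 accepts scores through the Week 24 visit: Week 20 dose date + 28, up to 3 days later, and not after the end-of-study date.
- No score completed after Day 1 enters baseline.
- State the WPAI entry day, or the date from which weeks are counted, and whether recall includes the completion day.

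With scores on Days 1, 8, … 169, a 28-day baseline then has 4 scores, month 1 uses Days 8, 15, 22 and 29 with no untreated days, and months 4-6 describe Days 85-168.

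Assigning scores by the midpoint of the recall window (completion date minus 4 days) looks attractive but is not advised. It presumes that recall excludes the completion day. It would also move scores dated Days 2 to 4 into baseline, although their recall includes post-dose days.

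This is a free improvement: a few sentences in the SAP and a small programming change before database lock, with no new data.
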